12.6.4.5.3 Vital Signs

Systolic and diastolic blood pressure, pulse rate and respiratory rate measured during the study will be listed by study visit, including low/normal/high results. Assessment after baseline will include change from baseline.

Descriptive statistics will be presented for systolic and diastolic blood pressure, pulse rate and respiratory rate at baseline, and on every subsequent day of the confinement period by actual exposure for each study day. Vital signs data will be summarized together with changes from baseline.

The data will be presented in the below outputs, the TFL number refers to the TFL number in the accompanying TFL shell document:

TFL number	Title
TABLES	
15.2.6.15	Summary of Supine Vital Signs – Safety Population
LISTINGS	
15.3.6.7	Listing of Vital Signs Data and Changes from Baseline

12.6.4.5.4 Spirometry

Spirometry parameters assessed during the study include:

- Measured forced expiratory volume in 1 second (FEV₁)
- Measured forced vital capacity (FVC)
- FEV₁/FVC
- Predicted FEV₁
- Percent of predicted FEV₁ (% pred)
- Predicted FVC
- Percent of predicted FVC (% pred)

- Measurement interpretation (categories: normal, abnormal, abnormal clinically significant)

The above data are collected at Screening, Day 0, and Day of Discharge (Day 6 or day of withdrawal). At Screening, data are collected prior and post-bronchodilator, also including the brand (trade) name and dose of the bronchodilator.

Spirometry predicted values will be standardized to the National Health and Nutrition Examination Survey III predicted set (**Hu and Cassano, 2000**).

Spirometry data values and normality evaluation will be listed by actual exposure and study day. Assessments performed after baseline (Day 0) will be listed together with change from baseline and shift in normality. Spirometry data from subjects who had significant clinical findings will be highlighted in listings.

Descriptive statistics will be presented for FEV₁(L), FEV₁ (% pred), FVC(L), FVC(% pred), and FEV₁/FVC at baseline, and Discharge by actual exposure, and overall. Spirometry data will be summarized together with changes from baseline (pre-bronchodilator), and the number and percentage of subjects with normal/abnormal/abnormal clinically significant results. The post-bronchodilator data will not be included in these summaries, they will only be listed.

The data will be presented in the below outputs, the TFL number refers to the TFL number in the accompanying TFL shell document:

TFL number	Title
TABLES	
15.2.6.17	Summary of Spirometry Results – Safety Population
LISTINGS	
15.3.6.8	Listing of Spirometry Data and Changes from Baseline

12.6.4.5.5 ECG

The ECG data will be obtained directly from the 12-lead ECG traces, i.e. not centrally read. These data include the PR, QT, and QT interval corrected using Bazett's formula (QTcB) intervals; QRS duration; and heart rate; and normality evaluation (normal, abnormal, clinically relevant, together with any PMI comments to the abnormality). In addition the QTcF value will be presented.

The baseline for the ECG data will be the Screening value.

ECG data values and normality evaluations will be listed by actual exposure and study day (Screening and Day 6) together with changes from baseline and shift in normality. ECG data from subjects which had significant clinical findings will be highlighted in listings.

Descriptive statistics will be presented for ECG data at baseline, and Day 6 by actual exposure. ECG data will be summarized together with changes from baseline, and the number and percentage of subjects with normal/abnormal/abnormal clinically significant results.

The data will be presented in the below outputs, the TFL number refers to the TFL number in the accompanying TFL shell document:

TFL number	Title
TABLES	
15.2.6.16	Summary of ECG Measurements – Safety Population
LISTINGS	
15.3.6.9	Listing of ECG Data and Changes from Baseline

12.6.4.5.6 Assessment of Cough

Cough questionnaire is assessed on a daily basis from Day 0 to Day 6. Questionnaire details are reported in Section 7.3.6 “Cough Assessment”.

The number and % of subjects reporting a cough will be summarized by actual exposure. The responses to the individual items, including the VAS evaluating the level of cough bother and 3 Likert scales measuring the intensity, the frequency of cough and the amount of sputum production will be listed and summarized on each day by study arm, for all subjects who filled in the questionnaire. The answers to the open question(s) related to any other important observation will be listed.

The data will be presented in the below outputs, the TFL number refers to the TFL number in the accompanying TFL shell document:

TFL number	Title
TABLES	
15.2.6.19	Summary of Cough Assessments Over Study – Safety Population
15.2.6.19.1	Summary of Cough Assessments by Study Day – Safety Population
LISTINGS	
15.3.6.14	Listing of Cough Assessment Results

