7.8.4.2 Assessment of Cough

Subjects will be asked to assess the respiratory symptom ‘cough’ on a VAS, on 3 Likert scales, and with an open question on a daily basis during the confinement period from Day 0 to Day 6. On each day, cough assessment has to be done prior to product use.

Subjects will be asked if they have experienced a regular need to cough, (e.g., whether they have coughed several times in the previous 24-hours prior to assessment). If the answer is ‘yes’, subjects will be asked to complete a VAS, 3 Likert scales, and to answer the open question.

On the VAS, subjects will assess how bothersome their cough was during the previous 24-hours. The VAS ranges from ‘not bothering me at all’ to ‘extremely bothersome’.

Furthermore, subjects will assess the intensity and frequency of cough and the amount of sputum production during the previous 24-hours on Likert scales.

The intensity of cough will be assessed on a 5-point Likert scale ranging from 1 to 5, with 1 = very mild - 2 = mild - 3 = moderate - 4 = severe - 5 = very severe.

The frequency of cough will be assessed on a 5-point Likert scale ranging from 1 to 5, with 1 = rarely - 2 = sometimes - 3 = fairly often - 4 = often - 5 = almost always.

The amount of sputum production will be assessed on a 4-point Likert scale ranging from 0 to 3, with 0 = no sputum - 1 = a moderate amount of sputum - 2 = a larger amount of sputum - 3 = a very large amount of sputum.

Finally, subjects will be asked with an open question if they want to share any other important observations with the staff about their coughing.

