12.5.4 Safety Analysis

In general, all safety data will be listed and tabulated on the safety population by product arm, using the approach described in Section 12.1.3. Safety variables collected during exposure periods will also be reported by product exposure.

Adverse event data will serve as the primary assessment of safety. Other safety variables monitored in this study include: respiratory symptoms (cough assessment VAS and Likert scales); vital signs (systolic and diastolic blood pressure, pulse rate, respiratory rate); spirometry; ECG data; clinical chemistry, hematology, concomitant medications, and urine analysis safety panel; physical examination.

Confidentiality statement: Data and information contained in this document are considered to constitute trade secrets and confidential commercial information, and the legal protections provided to such trade secrets and confidential information are hereby claimed under the applicable provisions of applicable law. No part of this document may be publicly disclosed without the written consent of Philip Morris Products S.A.

The number and percentage of subjects with AEs and SAEs will be tabulated by system organ class and preferred term. Summaries will also be presented for AEs leading to withdrawal, AEs leading to death, AEs by relatedness to product exposure, AEs by severity, and laboratory AEs. Tabulations will be performed for both the number of subjects experiencing an event and the number of events.

The number and percentage of subjects with clinical findings will be tabulated by sequence for laboratory parameters. Shift tables showing change from baseline of clinical findings will be provided for: ECGs, physical examinations, and laboratory parameters (both shifts in normal ranges and toxicity grades). Descriptive statistics will be summarized by visit and change from baseline for laboratory parameters, ECG, respiratory symptoms, and vital signs.

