7.3.6 Cough Assessment

Subjects will be asked to assess the respiratory symptom 'cough' using a VAS, three Likert scale questions, and one open ended question on a daily basis during the confinement period (on Day 0 to Day 6) prior to start of product use/smoking and no later than 10:00 PM. Although the symptoms are assessed on Days 0 to 6 the data reflects the

subjects respiratory symptoms from the previous day (Days -1 to Day 5) and therefore will be reported as Days -1 to Day 5 .

Subjects will be asked if they have experienced a regular need to cough, e.g., whether they have coughed several times in the previous 24 hours prior to assessment. If the answer is 'yes', subjects will be asked to complete questionnaire.

The VAS will assess how bothersome cough is to the subject ranging from 'not bothering me at all' to 'extremely bothersome', and this will be given a numeric value between 0 and 100, measured on a 100 mm scale.

Subjects will also be asked to assess the intensity and frequency of cough and the amount of sputum production on Likert scales as presented in **Table 7 “ Cough Assessment Likert Scales”**.

Table 7 Cough Assessment Likert Scales

Question	Likert Scale
1 The intensity of cough	1 = very mild 2 = mild 3 = moderate 4 = severe 5 = very severe
2 The frequency of cough	1 = rarely 2 = sometimes 3 = fairly often 4 = often 5 = almost always
3 The amount of sputum production	0 = no sputum 1 = a moderate amount of sputum; 2 = a larger amount of sputum; 3 = a very large amount of sputum.

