12.1.5 Handling of Dropouts or Missing Data (including outside the limits of quantification)

In general, missing data will not be imputed in this study, due to the nature of the measurements and the short periods of exposure and use. However, for questionnaire data total scores and domain or subscale scores may use a certain degree of imputation (by averaging across individual item scores) as detailed in Section 7.3 "Questionnaires".

Laboratory parameters will be presented as detailed in Section 7.1 "Biomarkers".

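### Cough severity is summarised each day only among subjects who report regular cough, so the scores are not comparable across days or arms, and the promised change from baseline is not planned

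*SAP*

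**What the plan says.** Cough is assessed every day from Day 0 to Day 6. The gate question is whether the subject had a regular need to cough, for example "whether they have coughed several times in the previous 24 hours prior to assessment" (SAP 7.3.6). After a 'yes', "subjects will be asked to complete a VAS, 3 Likert scales, and to answer the open question" (protocol 7.8.4.2); the SAP says in the same place that "subjects will be asked to complete questionnaire". So the questionnaire is what follows the gate.

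For the VAS, "this will be given a numeric value between 0 and 100, measured on a 100 mm scale". The intensity and frequency scales start at 1 (very mild, rarely) and have no category for absence of cough. The sputum scale has a zero, but it too is asked only after a 'yes'.

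SAP 12.6.4.5.6 plans two summaries. The first is prevalence: "The number and % of subjects reporting a cough will be summarized by actual exposure". The second covers the VAS and Likert items, "summarized on each day by study arm, for all subjects who filled in the questionnaire". No rule gives a 'no' answer a value, and SAP 12.1.5 states: "In general, missing data will not be imputed in this study".

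Protocol 12.5.4 says: "Descriptive statistics will be summarized by visit and change from baseline for laboratory parameters, ECG, respiratory symptoms, and vital signs". SAP 12.6.4.5.6 does not mention change from baseline for cough. SAP Section 9, which lists departures from the protocol analysis, does not mention dropping it.

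**The concern.** The item summaries condition on something that happens after randomization and may depend on the product. Who is in the denominator on a given day depends on who is coughing. A difference in mean VAS between THS 2.2, CC and SA, or between two days, therefore mixes a change in severity with a change in who contributes. If mild coughs resolve, the mean among those left goes up; if new mild coughs appear, it goes down.

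Change from baseline has the same problem. A subject who starts or stops coughing has no change score, and these are the subjects in whom something changed.

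This deserves attention although it is descriptive. Protocol 7.8.4 says that symptoms recorded on the questionnaires or VAS need not also be documented as AEs, because the questionnaire will be analysed in the final report; AE recording is left to the Investigator's discretion. For cough severity, the questionnaire summary is therefore the protocol's stated route to the report.

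**Working it through.** The documents give no cough prevalence, expected score or power for this endpoint, so there is no planned figure to reproduce. The check asks whether the planned statistic can move against the change in cough, and under what conditions.

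**Inputs.** N = 80 (planned THS 2.2 arm). Everything else is assumed: at baseline 20 subjects cough, 10 with VAS 10 and 10 with VAS 50.

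**Formulas.** With k subjects coughing and S the sum of their VAS scores, the planned mean is S/k and the proportion coughing is k/N. For comparison, S/N is the mean over all who answered if a 'no' is scored 0 by convention.

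| Scenario (assumed) | k | S | S/k | S/N | k/N |
|---|---|---|---|---|---|
| Baseline | 20 | 600 | 30.0 | 7.5 | 25.0% |
| 10 mild coughs resolve, the other 10 fall from 50 to 40 | 10 | 400 | 40.0 | 5.0 | 12.5% |
| Nothing resolves, 10 new coughs appear at VAS 10 | 30 | 700 | 23.3 | 8.75 | 37.5% |

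In the second row cough improves and the planned mean rises by 10. In the third row cough becomes more common and the planned mean falls by 6.7.

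**How far this depends on the assumptions.** With all 10 mild coughs resolved, the planned mean equals the final score of the persistent coughs. It therefore rises whenever that score is above 30. For final scores from 50 down to 25, S/N falls from 7.5 in every case, to between 500/80 = 6.25 and 250/80 = 3.125. If the persistent coughs fall to 45 and fewer mild coughs resolve:

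- none resolved: 550/20 = 27.5
- two resolved: 530/18 = 29.4
- four resolved: 510/16 = 31.9
- all ten resolved: 450/10 = 45.0

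So the reversal needs enough mild coughs to resolve. The results are the same for an arm of 40 with the same proportions.

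**Likert items.** Ten subjects at intensity 1 and ten at 3 give a mean of (10 + 30)/20 = 2.0. If the ten at 1 resolve, the mean becomes 3.0. Over all 80, with a 'no regular cough' category, the same data read 75.0% none, 12.5% very mild, 12.5% moderate at baseline, and then 87.5%, 0% and 12.5%. That display moves the right way and needs no assigned score.

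**Change from baseline.** In the second row only 10 of 80 subjects have a change score, each -10, while the planned daily mean goes up by 10. In the third row the 20 subjects coughing on both days have change 0, and the 10 new coughers have none.

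**The case against.** The strongest reply is that this is an ordinary two-part display: how many cough, then how bad it is among those who do. Much of that stands. A reader might infer that 'no' answers are thrown away. They are not: each one counts in the planned number and % reporting a cough. SAP 12.1.3 also requires n, quartiles, minimum and maximum. In the resolving-cough example a careful reader would see n fall from 20 to 10 and the maximum VAS fall from 50 to 40.

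A reader might also infer that a cough signal on THS 2.2 would be hidden. The documents do not support that. New cough raises the planned percentage, AEs are the primary safety assessment, and the Investigator may record questionnaire symptoms as AEs. The MNWS also has an ungated coughing item in all three arms, although SAP 12.6.3.1.3 lists individual answers and summarises only the total scores.

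A third tempting step is to equate 'no' with a VAS of 0. The gate asks about regular cough, not bother, so an occasional but bothersome cough would give a 'no'. Zero is a convention, and at the assumed baseline it would supply 60 of 80 values.

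Finally, table layouts sit in separate shells that were not available and may already show the number coughing beside the scores. The SAP text does not require it, and it groups prevalence by actual exposure but item scores by study arm.

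What remains is that prevalence beside the scores lets a reader suspect a changing group; it does not make severity comparable across days or arms.

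**Conclusion.** The point holds as a minor one. The item summaries rest on a group that changes daily and can differ by arm, so their means should not be compared across days or arms as measures of cough burden. The direction can be wrong: on the assumed values the mean among coughers rises from 30 to 40 while the proportion coughing halves. That size is illustrative only, and the reversal is not automatic.

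The missing change from baseline is a discrepancy between protocol and SAP that does not depend on the illustration. The shift-table entry in SAP Section 9 does not cover it. Protocol 12.5.4 planned shift tables for ECGs, physical examinations and laboratory parameters, and change from baseline for respiratory symptoms is a separate commitment.

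No test, threshold or decision depends on these tables. They are not in the safety-reporting set (SAP 13.2) or the topline set (SAP 13.3), and the primary conclusion is unaffected.

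**What to change.** In SAP 12.6.4.5.6:

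1. Tabulate intensity, frequency and sputum by day over all Safety Population subjects who answered the gate question, adding a 'no regular cough' category and taking percentages over all who answered. For sputum this category means not asked, so keep it apart from 'no sputum'.
2. Show change from baseline on that basis, for example the number and % in a better, the same or a worse category than at baseline. If it is to be dropped instead, say so in Section 9.
3. Put the number and % coughing in the same table, under one grouping for both parts.
4. Keep the coughers-only VAS and item scores, labelled as conditional on cough. Any VAS summary with 'no' scored 0 should be supplementary and stated as a convention.

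The cost is SAP wording, matching changes to the table shells and slightly larger tables. Items 1 to 3 use only answers already collected. The optional VAS display adds one labelled convention.

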13 ANALYSIS AND REPORTING

13.1 Interim Analysis and Data Monitoring

No interim analysis is planned on this study.

A Clinical Research Associate (“Monitor”) from [REDACTED] will be responsible for the monitoring of the study. Monitoring will be performed according to [REDACTED] standard operating procedures (SOPs) and as per the agreed monitoring plan with PMI.

The PI, or a designated member of the PI's staff, must be available during the monitoring visit to review the data and resolve any queries, and to allow direct access to the subject's records for source data verification.

All changes to the source data will have to be approved by the PI.

13.2 Safety Reporting

Statistical summaries required for safety reporting will be made available to PMI medical safety officer following database lock. The TFLs are listed in the table below.

TFL no.	Title
TABLES	
15.2.1.4.1	Summary of Demographics and Other Baseline Characteristics – Safety Population
15.2.1.4.2	Summary of Demographics and Other Baseline Characteristics – FAS
15.2.1.4.2.1	Summary of Demographics and Other Baseline Characteristics by Sex – FAS
15.2.1.4.2.2	Summary of Demographics and Other Baseline Characteristics by Cigarette Consumption – FAS
15.2.2.1	Summary of Use of THS 2.2 Product and CC – Safety Population
15.2.6.1	Summary of Adverse Events – Safety Population
15.2.6.2.1	Summary of Adverse Events by System Organ Class and Preferred Term – Safety Population
15.2.6.3	Summary of Adverse Events by System Organ Class, Preferred Term and Relationship to Study Product Exposure and Expectedness – Safety Population
15.2.6.4	Summary of Adverse Events Leading to Study Product Discontinuation or Reduction by System Organ Class and Preferred Term – Safety Population
15.2.6.5	Summary of Adverse Events Leading to Study Discontinuation by System Organ Class and Preferred Term – Safety Population
15.2.6.6	Summary of Adverse Events Related to Study Procedure by System Organ Class and Preferred Term – Safety Population
15.2.6.7	Summary of Adverse Events by System Organ Class, Preferred Term and Severity – Safety Population
15.2.6.8	Summary of Serious Adverse Events – Safety Population
15.2.6.9	Summary of THS 2.2 Device Events – Safety Population
15.2.6.9	Summary of THS 2.2 Device Events – Safety Population

13.3 Topline Results

Topline results, delivered with the draft TFLs, are composed of key statistics and study results listings, will be made available to PMI management following database lock and prior to completion of the complete set of TFLs. The topline results are listed in the table below.

TFL no.	Title
FIGURES	
15.1.1.1	Blood COHb (%) Mean and 95% CI– FAS
15.1.1.2	MHBMA Urinary Concentration Adjusted for Creatinine Mean and 95% CI– FAS
15.1.1.3	3-HPMA Urinary Concentration Adjusted for Creatinine Mean and 95% CI– FAS
15.1.1.4	S-PMA Urinary Concentration Adjusted for Creatinine Mean and 95% CI– FAS
TABLES	
15.2.3.1	Analysis of Primary Biomarkers of Exposure versus CC – FAS
15.2.3.2	Descriptive Statistics of % Change in Primary Biomarkers on Day 5 – FAS
15.2.3.2.1	Descriptive Statistics of % Change in Primary Biomarkers on Day 5 by Sex – FAS
15.2.3.2.2	Descriptive Statistics of % Change in Primary Biomarkers on Day 5 by Cigarette Consumption – FAS
15.2.3.3	Descriptive Statistics of Blood COHb (%) – FAS
15.2.3.4	Descriptive Statistics of MHBMA Urinary Concentration Adjusted for Creatinine (units) – FAS
15.2.3.4.1	Descriptive Statistics of MHBMA Urinary Concentration Adjusted for Creatinine (units) by Sex – FAS
15.2.3.4.2	Descriptive Statistics of MHBMA Urinary Concentration Adjusted for Creatinine (units) by Cigarette Consumption – FAS
15.2.3.5	Descriptive Statistics of 3-HPMA Urinary Concentration Adjusted for Creatinine (units) – FAS
15.2.3.5.1	Descriptive Statistics of 3-HPMA Urinary Concentration Adjusted for Creatinine (units) by Sex – FAS
15.2.3.5.2	Descriptive Statistics of 3-HPMA Urinary Concentration Adjusted for Creatinine (units) by Cigarette Consumption – FAS
15.2.3.6	Descriptive Statistics of SPMA Urinary Concentration Adjusted for Creatinine (units) – FAS
15.2.3.6.1	Descriptive Statistics of SPMA Urinary Concentration Adjusted for Creatinine (units) by Sex – FAS
15.2.3.6.2	Descriptive Statistics of SPMA Urinary Concentration Adjusted for Creatinine (units) by Cigarette Consumption – FAS
15.2.4.1	Analysis of Primary Biomarkers of Exposure versus SA – FAS
15.2.4.2	Analysis of Urinary Quantity Excreted of MHBMA, 3-HPMA and SPMA over 24 hours – FAS
15.2.4.3	Descriptive Statistics of Urinary Quantity Excreted of MHBMA over 24 hours (units) – FAS
15.2.4.4	Descriptive Statistics of Urinary Quantity Excreted of 3-HPMA over 24 hours (units) – FAS
15.2.4.5	Descriptive Statistics of Urinary Quantity Excreted of SPMA over 24 hours (units) – FAS

TFL no.	Title
15.2.1.4.1	Summary of Demographics and Other Baseline Characteristics – Safety Population
15.2.1.4.2	Summary of Demographics and Other Baseline Characteristics – FAS
15.2.1.4.2.1	Summary of Demographics and Other Baseline Characteristics by Sex – FAS
15.2.1.4.2.2	Summary of Demographics and Other Baseline Characteristics by Cigarette Consumption – FAS
15.2.6.1	Summary of Adverse Events – Safety Population
15.2.6.2.1	Summary of Adverse Events by System Organ Class and Preferred Term – Safety Population
15.2.6.2.2	Summary of Adverse Events by System Organ Class – Safety Population
15.2.6.2.3	Summary of Adverse Events by Preferred Term – Safety Population
15.2.6.3	Summary of Adverse Events by System Organ Class, Preferred Term and Relationship to Study Product Exposure and Expectedness – Safety Population
15.2.6.4	Summary of Adverse Events Leading to Study Product Discontinuation or Reduction by System Organ Class and Preferred Term – Safety Population
15.2.6.5	Summary of Adverse Events Leading to Study Discontinuation by System Organ Class and Preferred Term – Safety Population
15.2.6.6	Summary of Adverse Events Related to Study Procedure by System Organ Class and Preferred Term – Safety Population
15.2.6.7	Summary of Adverse Events by System Organ Class, Preferred Term and Severity – Safety Population
15.2.6.8	Summary of Serious Adverse Events – Safety Population

